The rise in the number of adult orthodontic patients has increased demand for aesthetic and comfortable alternatives to traditional fixed appliances. Clear aligners that meet this demand are also vulnerable to rapid technological advancements in aligner materials and manufacturing techniques. The removable appliance was used solely to move teeth in the first generation of aligners. Following that, a second generation of aligners was developed that relied more on attachments bonded to teeth. The most

recent, third generation, has been modified to automatically place various types of attachments where difficult tooth movements are required. These technology advancements have increased the number and complexity of cases treated with this method.^(4,5)

Since the introduction of Invisalign in 1997, treatment with clear aligners has become a rapidly growing sector in orthodontics. Clear aligners offer more aesthetically pleasing and comfortable treatment experience, improve oral hygiene, cause less pain than fixed orthodontic appliances, reduce the number and duration of appointments, and necessitate fewer emergency visits. However, the cost of production, reliance on patient cooperation, and inability to treat certain malocclusions limit their use.^(6,7)

Orthodontic treatment typically lasts between 24 and 36 months. In general, patients reject this treatment modality due to the lengthy treatment period. In extended treatment protocols, root resorption, caries, and decreased patient compliance are more common. As a result, accelerating orthodontic tooth movement is appropriate to avoid those side effects and can encourage patients to complete the treatment. Acceleration of orthodontic tooth movement (OTM) has been used successfully to reduce levelling and alignment time using surgical interventions such as corticotomy, corticision, piezocision, and micro-osteoperforation.^(6,8)

Orthodontic treatment is generally based on the rule of bone remodeling that occurs as a result of applying forces to a tooth, creating areas of tension and pressure on the periodontal ligament. The events that lead to tooth movement are intricate, incorporating interactions between cells in the alveolar bone and the periodontal ligament. The process is characterized by acute inflammation, followed by chronic inflammation, and then by acute inflammation (after reactivation of orthodontic forces). These changes in periodontal tissues cause bone remodeling, which is necessary for orthodontic tooth movement. Many studies have now been conducted to investigate various methods of accelerating tooth movement, such as drug injections, electric

stimulation, corticotomy, pulsed electromagnetic fields, and mechanical and physical methods. ^(6,9)

Low-Level Laser Therapy is one of these interventions (LLLT). Low-Level Laser (LLL) has analgesic, anti-inflammatory, and bio stimulatory properties. Among all methods studied to accelerate induced dental movement and thus reduce orthodontic treatment time, Low-Level Laser is the least invasive, easiest, safest, and fastest to apply. Initially, histological studies revealed that LLLT promotes remodeling processes in alveolar bone by increasing the number of osteoblasts and osteoclasts. As a result, there has been an exponential increase in the number of studies conducted to investigate the effectiveness of laser treatment in accelerating tooth movement. LLLT, on the other hand, has a high patient acceptability and is simple to use, especially with the availability of small portable devices. ^(10,11)

Low-Level Laser Therapy (LLLT) is a simple, localized, nonsurgical, noninvasive method with no side effects that is gaining popularity among OTM researchers. LLLT has been shown in numerous studies to improve vascularization, collagen fiber organization, and osteoblastic activity. ⁽¹²⁾

Laser is an abbreviation for "light amplification by simulated emission of radiation," one of the greatest technological advances of the twentieth century. Lasers were first used in medicine in 1963. One year later, the first laser applications in the field of dentistry were performed using a ruby laser on hard issues. ⁽¹³⁾

The effects of LLLT on tooth movement were studied in both clinical and animal studies. Numerous human studies have shown that LLLT can simulate the velocity of tooth movement. At that point, it is emphasized that the effects of laser application on bio simulation is dose dependent. ⁽¹³⁾

By reviewing the available Literature , little studies demonstrated the acceleration of orthodontic tooth movement by aligner associated with LLLT , so the goal of the

present study is directed to evaluate the rate of correction of lower incisor crowding by clear aligner and LLLT versus clear aligner alone .

Aim of the study :

The present study will be performed to evaluate the effect of low-level laser therapy (LLLT) on the rate of orthodontic tooth movement through the correction of lower incisors crowding using clear aligners .

Subjects and methods :

Patients with lower anterior mild to moderate crowding will be collected from AlAzhar University from Faculty of Dental Medicine for Girls and post records will be collected after relieve of crowding .

Study design: Randomized Control Study.

Randomization will be done by using Microsoft Office Excel 2007 . patients information will be entered into a computer ,then the computer randomly assigns the patients to two groups that helping to prevent bias.

Control group (n=11) patients will receive a conventional therapy with clear aligners and the investigational group (n=11) will receive the new treatment therapy by using clear aligners for the treatment of mild to moderate lower anterior crowding with laser acceleration .

Sample size calculation⁽¹⁴⁾:

This power analysis used leveling and alignment improving % as the primary outcome. Based upon the results of . AlSayed Hassan MMAA et al (7102); the mean (Standard deviation) values were 89.42 (7.16) and 71.7 (16.18) %, respectively. The effect size (d) was 1.416. Using alpha (α) level of (5%), β level of 0.8 (Power = 80%); the minimum estimated sample size was 9 subjects per group. Sample size was increased to 11 subjects per group to compensate for a dropout rate of 20% after 6 months. Sample size calculation was performed using G*Power version 3.1.9.2.

Ethical approval:

The research protocol approved by ethical committee of Faculty of Dental Medicine, girls, Al-Azhar University, (P-OR-22-05). The steps of the procedure will be explained to the patients / parents and an informed consent will be signed

Inclusion criteria⁽¹⁵⁾:

1. A well-behaved, compliant, and motivated patient.
2. Patients from 16 to 23 years old .
3. Patients with mild to moderate anterior lower crowding.
4. Full complement of teeth (except for wisdom teeth).
5. Class I Angle malocclusion .

Exclusion criteria⁽¹⁶⁾:

1. Patients with missed anterior teeth .
2. Class II or III Malocclusion (dental or skeletal) .
3. Any systemic diseases that may interfere with assigned treatment plan .
4. Periodontal affection especially at lower anterior teeth .

Method:

Each patient will have the following record taken before the delivery

:

- Orthodontic casts (upper and lower).
- Photography, both intraoral and extraoral ○ lateral cephalometric X-ray .
- Panoramic X-ray

Treatment groups:

The sample will be divided into two groups according to laser application, 11 patients each group :

Group (A): Clear aligners will be used to treat patients with lower anterior crowding with low level laser acceleration .

Group (B): Clear aligners will be used to treat patients with lower anterior crowding without laser acceleration .

Statistical analysis :

Measurements will be taken and the collected data will be tabulated and analyzed statistically.

References:

1. **Das P. J. , Dkhar W. , Pradhan A.** . An Evaluation of Dental Crowding in Relation to the Mesiodistal Crown Widths and Arch Dimensions in Southern Indian Population . *JCDR*.2017;11:01-3.
2. **Jaber S. T., Hajeer M. Y., Burhan A. S. & Latifeh, Y.** . The Effect of Treatment With Clear Aligners Versus Fixed Appliances on Oral Health-Related Quality of Life in Patients With Severe Crowding: A One-Year Follow-Up Randomized Controlled Clinical Trial .*cureus* .2022;14: 1-26.
3. **Nüser C. , Jung K. , Helms H. J. , Engelke W. , Sandoval P.** .Interaction between deglutition, tongue posture, and malocclusion: A comparison of intraoral compartment formation in subjects with neutral occlusion or different types of malocclusion . *Angle Orthod*. 2016 ;86:697-705 .
4. **Tamer I. , Öztaş E. , Marşan G.** . Orthodontic Treatment with Clear Aligners and The Scientific Reality Behind Their Marketing: A Literature Review . *TurkJOrthod*.2019;32:741-6 .
5. **Hennessya J. , Garveyb R. S. , Al-Awadhib E. A.** . A randomized clinical trial comparing mandibular incisor proclination produced by fixed labial appliances and clear aligners . *Angle Orthod* .2016;86:706-12 .

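### The aim is a rate, but the primary outcome is an untimed percentage, and the only post-treatment record is taken once crowding is relieved

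*Combined protocol and SAP*

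**What the plan says.** The sentence before the section Aim of the study gives the goal as evaluating "the rate of correction of lower incisor crowding by clear aligner and LLLT versus clear aligner alone". The Aim section also speaks of a rate. The background explains why speed matters: surgical acceleration "has been used successfully to reduce levelling and alignment time", and low-level laser is introduced among the methods studied to "accelerate induced dental movement and thus reduce orthodontic treatment time".

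The outcome is named once, under Sample size calculation: "This power analysis used leveling and alignment improving % as the primary outcome". No index, formula, unit of time or assessment time accompanies it. The planning "values were 89.42 (7.16) and 71.7 (16.18) %, respectively".

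Two sets of records are specified. Under Method: "Each patient will have the following record taken before the delivery". Under Subjects and methods: "post records will be collected after relieve of crowding". No interim record, common assessment date or recording of elapsed time is described.

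The section Statistical analysis reads in full: "Measurements will be taken and the collected data will be tabulated and analyzed statistically". The only duration given for this trial is 6 months, which appears under Sample size calculation as the horizon for the 20% dropout allowance.

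**The concern.** A rate needs a time. It can be measured as change by a fixed time, as time to a fixed state, or as change divided by elapsed time. The plan sets up none of these. Its outcome is a percentage without a time, and its one timing rule for post-treatment records is triggered by the event that the laser is meant to bring forward.

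Recording each patient on reaching relief holds the end state roughly constant and lets the time vary. A percentage read at that point discards the time, which is where the laser effect would lie. A laser that truly speeds movement could then look ineffective, and the stated power would describe a different measurement. If a reading before relief is intended, the time is missing and could be chosen after data are seen. Dates or fixed-time records that are not collected during the trial may be impossible to recover.

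**Working it through.** **1. The plan's own figure.** Inputs from Sample size calculation: means 89.42 and 71.7, SDs 7.16 and 16.18, alpha 5%, power 80%.

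- Difference: 89.42 − 71.7 = 17.72 points.
- Common SD: √[(7.16² + 16.18²)/2] = √[(51.27 + 261.79)/2] = 12.51.
- d = 17.72/12.51 = 1.416, as stated.
- A two-sided two-sample t-test needs n = 8.90, so 9 per group, with power 80.5% at 9. The plan's figure is reproduced.

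**2. Do the planning means fit a reading at relief?** The crowding left is 100 − 89.42 = 10.58% in one arm and 100 − 71.7 = 28.3% in the other, a ratio of 28.3/10.58 = 2.67. One arm would be called relieved with 2.7 times as much crowding left. A reading at a common time before relief explains these means more easily.

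**3. Power if the gap shrinks.** The documents give no gap at relief, so a range of 0 to 5 points is assumed. Two-sided t-test, 9 per arm:

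| Gap (points) | Power, SD 12.51 | Power, SD 7.16 |
|---|---|---|
| 17.72 (planned) | 80.5% | 99.8% |
| 5 | 12.5% | 28.6% |
| 2 | 6.2% | 8.6% |
| 1 | 5.3% | 5.9% |
| 0 | 5% | 5% |

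**4. How small might the gap be?** This was simulated under assumptions that are not in the documents:

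- Each patient's percentage v at a reference time (t = 1, the time to which the planning values apply) is drawn from the planning means and SDs.
- The path is linear, v × t capped at 100%, or exponential, 100 × (1 − exp(−k × t)) with k = −ln(1 − v/100).
- Relief is the first check at or above 85, 90 or 95%, with checks every 1/12 or 1/6 of the reference time.
- Measurement error has SD 2 points; 9 per arm; t-test.

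Results over these settings:

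- Percentage at relief: gap about 0.2 to 1.7 points, power roughly 5 to 15%.
- Time to relief in the same simulated patients: power about 75 to 83%.
- Percentage at relief with no measurement error: power about 6 to 13% (linear) or 18 to 31% (exponential).

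The information on speed is present in these patients; the percentage at relief does not carry it.

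**5. A reading at one common time.** Same assumptions, error SD 2:

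| Multiple of reference time | Power, linear | Power, exponential |
|---|---|---|
| 1.0 | 83% | 83–85% |
| 1.2 | 85% | not tabulated |
| 1.3 | 69% | not tabulated |
| 1.4 | 44% | not tabulated |
| 1.6 | 12% | 83% |
| 2.0 | not tabulated | 77% |

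On the linear path the fall comes from the ceiling. At 1.4 times, the uncapped control mean would be 71.7 × 1.4 = 100.4%, so many control patients have also finished. A common time helps only if it is early enough.

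**The case against.** The strongest answer is that the sponsor always meant a common-time reading. The planning means point that way, and the 6-month figure may be the intended horizon. The sentence about post records does not say that those records supply the primary outcome. On this view the defect is one unstated time point, and the power loss belongs to a reading nobody intended.

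Much of this stands. The documents do not say which record feeds the outcome, so the loss of power is conditional. The 6-month phrase, however, qualifies dropout and defines no measurement. If it was meant as the assessment time, the plan must say so and reconcile it with records triggered by relief. Taken literally, the plan specifies only one post-treatment record, and that one falls at the wrong moment for an untimed percentage.

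It is also fair to say that the simulation rests on assumed paths, thresholds, checks and error. The exponential result roughly doubles without measurement error, and the figures would change if the crowding left at relief differed by arm. They show direction and rough size only.

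A reader might go further and infer that the trial cannot detect acceleration, or that its sample size is miscalculated. The documents support neither. The first would require the outcome to be fixed to the relief record, which is not stated, and the sample size arithmetic reproduces.

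**Conclusion.** The point holds in conditional form. It is certain from the text that the aim is a rate, that the primary outcome has no time element or assessment time, and that the only post-treatment record is triggered by relief. If the outcome is taken from that record, the 80% power no longer applies, and roughly 5 to 15% is a reasonable indication under the stated assumptions, including the 2-point error. If a reading before relief is intended, the planning values are easier to understand, but the time that gives them meaning is absent. On either reading, the plan does not yet define a measurement that answers its question. This should be settled before outcome data are collected. Confidence in the gap is high; confidence in the size of the power loss is moderate at best.

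**What to change.** **Preferred.** State whether 6 months was meant as the assessment time. Then take the post record from every randomised patient at one pre-stated common time before full alignment is expected, and make percentage improvement at that time the primary outcome. Give the index and formula. Justify the time (6 months, if that was intended) against the time to which the planning values apply, because too late a reading loses the difference.

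Cost: one fixed-time record per patient. The present power statement can be kept only if the chosen time is justified. The record at relief is lost unless one more is taken.

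**Alternative.** Keep the record at relief. Record the dates of aligner delivery and of relief, define relief by one pre-stated criterion checked at the same interval in both arms, and make time from delivery to relief the primary outcome. Include all randomised patients, censor those not relieved, and restate the power for this outcome.

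Cost: two dates per patient and regular checks, which may add visits or records, plus a new power calculation for which the documents give no time data.

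### The only post-treatment record is triggered by success and dropout is met only by extra enrolment, so patients still crowded or lost early have no planned outcome

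*Combined protocol and SAP*

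**What the plan says.** Subjects and methods gives the only post-treatment record in the document, and its timing is an outcome, not a date: "post records will be collected after relieve of crowding". The Method section lists only the records taken before the appliance is delivered. No calendar visit is set for the final record, and nothing says what is recorded for a patient whose crowding is not relieved or who stops early.

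The outcome used for power is a percentage: "This power analysis used leveling and alignment improving % as the primary outcome". Dropout is mentioned once, under Sample size calculation: "Sample size was increased to 11 subjects per group to compensate for a dropout rate of 20% after 6 months".

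The Statistical analysis section is one sentence: "Measurements will be taken and the collected data will be tabulated and analyzed statistically". It names no analysis population, missing-data rule or censoring rule.

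**The concern.** If the final record is taken only once crowding is relieved, whether a patient has an outcome depends on how well that patient did. A patient who leaves early or remains crowded has a baseline cast but no planned second one, and so contributes nothing to a percentage improvement. What remains is a comparison among patients who succeeded, which is no longer protected by randomisation. Going from 9 to 11 per group restores the count, but not the comparability of those left.

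The loss could also differ by arm. If follow-up ends at relief, a slower arm is followed longer and has more time to lose patients. The protocol's own introduction links long treatment to poorer compliance and suggests that acceleration helps patients finish, so this route is plausible on the trial's own rationale. Leaving out the slowest patients raises the mean most in the arm with the wider spread. With the planning values that is the lower-mean arm, so the observed laser effect would shrink.

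**Working it through.** **Inputs from Sample size calculation.** "the mean (Standard deviation) values were 89.42 (7.16) and 71.7 (16.18) %, respectively"; "The effect size (d) was 1.416"; 9 per group raised to 11; 20% dropout after 6 months. The text does not label the two means by arm. I take the higher as laser.

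**The plan's own figures.** The SD is √((7.16² + 16.18²)/2) = 12.51 and the difference is 89.42 − 71.7 = 17.72, so d = 17.72/12.51 = 1.416, as stated. A two-sided two-sample t-test has 75.0% power at 8 per group and 80.5% at 9, so 9 reproduces. For dropout, 9 × 1.2 = 10.8, rounded up to 11. (Dividing, 9/0.8 = 11.25, would round up to 12; nothing here turns on that.) At 20% loss, 11 × 0.8 = 8.8 per group are expected to remain.

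**How different could loss be between arms?** The following are assumptions, not in the documents: a constant dropout rate that reaches 20% at 6 months, follow-up ending at relief, and relief at 4 months with laser and 6 months without.
- Monthly rate: −ln(0.8)/6 = 0.0372.
- Loss by 4 months: 1 − exp(−4 × 0.0372) = 13.8%, or 11 × 0.138 = 1.5 patients.
- Loss by 6 months: 20%, or 2.2 patients.
- Gap: about 0.7 of a patient per arm.

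With the control arm relieved at 6 months, a laser arm 10%, 30% or 50% faster loses 18.2%, 14.5% or 10.6%. The gap then runs from about 0.2 to 1.0 of 11 patients. With no laser effect it is zero.

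**What would selective loss do to the planned difference?** This is an illustration for percentage improvement read at a common time, normally distributed, in the extreme case where exactly the slowest patients are lost. Losing the lowest fraction p of a normal distribution raises the mean by SD × φ(z)/(1 − p), where z is the p-quantile.
- p = 20%: φ(−0.842)/0.8 = 0.350. Lower-mean arm: 16.18 × 0.350 = +5.66. Higher-mean arm: 7.16 × 0.350 = +2.51.
- p = 13.8%: φ(−1.088)/0.862 = 0.256. Higher-mean arm: 7.16 × 0.256 = +1.83.

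| Loss, higher-mean / lower-mean arm | Observed difference (points) |
|---|---|
| none | 17.72 |
| 20% / 20%, slowest lost | 17.72 + 2.51 − 5.66 ≈ 14.6 |
| 13.8% / 20%, slowest lost | 17.72 + 1.83 − 5.66 ≈ 13.9 |
| any, unrelated to progress | 17.72 expected |

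Most of the shift comes from equal loss acting on unequal SDs. The difference in loss between arms adds about 0.7 point.

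**If time to relief were the outcome.** A simulation with an assumed control mean of 5 months, a coefficient of variation (CV) of 0.3 and a true laser/control time ratio of 0.70 gives a completers-only ratio of 0.703 when everyone else is followed until relief. If recording stops at 6 months, the ratio is 0.78, with 66% of control and 86% of laser patients observed. With CVs of 0.2 to 0.4, the 6-month stop gives 0.74 to 0.80.

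**The case against.** The strongest reply is that the protocol is silent here and does not state an exclusion. The sentence on post records says when they are taken; nowhere does the document say that unrelieved patients are left out, that observation stops at relief, or that treatment has a cut-off. Eligibility is limited to mild to moderate Class I crowding in motivated, compliant patients, so few may remain crowded. If everyone is followed to relief, the simulation above shows negligible bias in the time ratio. All this stands. It lowers the likely size, but it does not give a patient who leaves, or who is never relieved, a planned outcome.

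A reader might infer that the slower arm will lose more patients. The documents do not support that as a fact: they neither state nor predict unequal dropout, and the inference needs a real laser effect, dropout that builds with time and follow-up that ends at relief.

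A reader might also bound the bias by putting 20% loss in one arm and none in the other. Nothing in the plan, nor the constant-rate assumption used above, produces that split.

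Finally, the point estimates above presuppose a common reading time. If every record really is taken at relief, improvement would be near its ceiling in both arms and a 17.7-point difference would not be what is observed. That objection is correct; it is why the figures are offered only as an illustration, and why this point should be settled together with when the outcome is read.

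**Conclusion.** The point holds in a limited form. Followed as written, the plan provides an outcome only for patients who reach relief, and it answers dropout with numbers alone. That creates a risk of selection; it does not show that the comparison will be confined to successes.

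The expected difference in loss between arms is small, under one patient of 11 at the assumed 4 and 6 months. In the extreme case where exactly the slowest leave, the planned difference falls by about 18% (to 14.6) or 22% (to 13.9), given the planning means and SDs, normality and a common reading time. If loss is unrelated to progress there is no bias. This is a cheap improvement that has to be made before data collection, because a cast that was never taken cannot be recovered.

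**What to change.** 1. Take the post record for percentage improvement from every randomised patient, relieved or not, at one pre-specified common time. The 6-month horizon already used for dropout is an obvious candidate. Reading relieved patients at relief and the others at a fixed time would leave the reading time dependent on the outcome.
2. Invite patients who stop treatment to attend that same visit.
3. Analyse all randomised patients in their assigned arm. If time to relief is used instead, censor unrelieved patients at last observation.
4. Do not use a record taken at withdrawal as the final value in the main analysis, since that amounts to carrying the last observation forward. Keep it for a sensitivity analysis.
5. State how outcomes that remain missing will be handled, and report losses and reasons by arm.

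The cost is a few sentences in the protocol and a final cast for a few more patients: about 22 × 0.2 = 4 dropouts, plus any who are still crowded. Some who leave will not return, so some outcomes will still be missing.

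### Does the missing rule linking Excel randomization to 11 and 11 patients undermine the allocation?

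*Combined protocol and SAP*

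**What the plan says.** The allocation method stands in Subjects and methods, under Study design. The tool is named ("Randomization will be done by using Microsoft Office Excel 2007") and the order of steps is given: "patients information will be entered into a computer ,then the computer randomly assigns the patients to two groups that helping to prevent bias". The next paragraph fixes the sizes: "Control group (n=11) patients will receive a conventional therapy with clear aligners", and "the investigational group (n=11) will receive the new treatment therapy".

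Two other sections bear on the point. Treatment groups says "The sample will be divided into two groups according to laser application, 11 patients each group". Sample size calculation explains where the totals come from: "the minimum estimated sample size was 9 subjects per group", raised to 11 for dropout. The Method section times the baseline records: "Each patient will have the following record taken before the delivery".

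The text available for review does not state the rule that yields equal groups, whether patients are assigned one at a time or all together, who makes the draw, or that entry and draw cannot be reversed.

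**The concern.** A random draw and a fixed total of 11 per group do not by themselves define one procedure. Independent tosses usually miss 11:11, so some further rule must operate, and the possible rules differ in how far they protect the allocation.

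- One shuffle of a complete list leaves nothing to foresee.
- Tossing one by one until an arm is full makes the last assignments known to anyone who keeps count.
- Repeating the draw until the sizes match is harmless if size is the only reason for repeating. Without a record, it cannot be told apart from repeating for another reason.

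The stake is selection at entry. The first inclusion criterion (good behaviour, compliance and motivation) is a judgement, and an enroller who could foresee the next arm might apply it differently. With 22 patients, a few steered entries would matter, and no analysis repairs that afterwards. The timing of baseline records relative to delivery, with no mention of assignment, seems to add to the looseness.

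**Working it through.** **Inputs.** Group sizes 11 and 11 (Study design; Treatment groups). From Sample size calculation: "the mean (Standard deviation) values were 89.42 (7.16) and 71.7 (16.18) %, respectively", d = 1.416, alpha 5%, power 80%, 9 per group. The protocol does not say whether the test is two-sided; two-sided is assumed because it reproduces the 9.

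**1. The plan's own figures.** The pooled SD is √[(7.16² + 16.18²)/2] = 12.51, so d = (89.42 − 71.7)/12.51 = 1.416, as stated. A two-sided t test has power 0.750 at 8 per group and 0.805 at 9, so 9 is reproduced.

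**2. Independent tosses (assumed; not stated in the protocol).** With 22 patients and probability ½:

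- P(11:11) = C(22,11)/2²² = 705,432/4,194,304 = 0.168
- P(9:13 or more uneven) = 0.523
- P(one arm at 8 or fewer) = 0.286
- Mean number of draws to reach 11:11 = 1/0.168 = 5.9

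These figures describe a procedure that does not deliver fixed totals. It is therefore the reading that fits the protocol least.

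**3. Does an arm below 9 matter?** Nine per group is a requirement for equal groups totalling 18. It is not a floor for the smaller arm of a trial of 22. The noncentrality is d·√[n₁n₂/(n₁ + n₂)] with 20 degrees of freedom:

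| Split | Noncentrality | Power |
|---|---|---|
| 11:11 | 3.321 | 0.884 |
| 9:13 | 3.265 | 0.874 |
| 8:14 | 3.195 | 0.860 |
| 7:15 | 3.093 | 0.837 |
| 6:16 | 2.958 | 0.803 |
| 5:17 | 2.783 | 0.754 |

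Before dropout, power falls below 80% only at 5:17 or worse, which independent tosses would give in 1.7% of trials. Averaged over all splits, power is 0.868 against 0.884, a loss of under 2 points. If dropout left 18 patients, power would be 0.805 at 9:9, 0.800 at 8:10 and 0.785 at 7:11, so imbalance still costs little.

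**4. Foreseeability, if assignment is one by one.** By exact recursion for an observer who knows all earlier assignments:

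- Toss capped at 11 per arm: the last 3.70 assignments are forced on average. Correct guesses are (18.3 × 0.5 + 3.7)/22 = 58%.
- One shuffled list of 11 and 11, opened in order: the last 22/12 = 1.83 are forced. Correct guesses are 13.47/22 = 61%.
- One shuffle after all patients are entered: no assignment can be foreseen at entry.

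The first two apply only if patients are assigned singly, which the protocol does not say.

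**5. Repeated draws (inputs assumed).** If someone kept the best-looking of 3 to 5 draws, and visible prognosis correlated 0.3 to 0.5 with outcome, simulation puts the two-sided 5% error at 5.2% to 7.1% and the laser-favouring 2.5% error at about 4% to 7%. A single draw gives 5.0% and 2.5%. The protocol supplies neither a number of draws nor a correlation.

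**6. The sections side by side.** Study design puts data entry before assignment. Treatment groups divides one sample into two sets of 11. Together they describe entering the patients and then splitting them once. Records taken before delivery are compatible with records taken before assignment.

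**The case for a change.** The strongest case for a change is that the protocol relies on randomization to prevent bias, and that protection depends on the details left out. Two teams following the text could run procedures that differ in foreseeability. The remedy also looks cheap: a paragraph naming the rule, the operator and a single saved draw.

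The omission is real, and that part of the case stands. A capped one-by-one assignment run by the enroller would be weaker than a single shuffle, and the text does not exclude it.

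Two parts do not stand. The coin-toss probabilities measure a scheme at odds with the stated totals, and the suggestion of harm from an arm below 9 is answered by the power table. The stronger form of the remedy, holding every patient until all 22 are registered, has a price that cannot be worked out because no recruitment period is given. Assigning patients as they arrive avoids the wait, but any rule that ends at exactly 11:11 then stays partly guessable. That is a trade-off, and the protocol is not in error for leaving it open.

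**Conclusion.** No change to the plan follows. The protocol leaves out the rule, the operator and the finality of the draw, but its steps, followed in the order written, give a valid random allocation, and its wording fits one shuffle into 11 and 11. A written clarification would mainly record that procedure.

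No effect on the trial's error rate can be established from the documents; the 5.2% to 7.1% range rests wholly on assumed misuse. The effect on power is small even under the least plausible reading: 0.868 on average against 0.884. Both power figures assume the planned d of 1.416, a two-sided t test and no dropout.

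The conclusion depends on the draw being made once after entry. If the trial records showed repeated draws, or one-by-one assignment by someone who could see the running count, the question would need to be reopened. It is also limited to the text available for review.

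### Minor: 11 per group does not quite keep the stated minimum of 9 after 20% dropout (8.8 expected, about 1 point of power)

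*Combined protocol and SAP*

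**What the plan says.** Under the sample size heading, the plan takes levelling and alignment improvement (%) as the primary outcome. It cites an earlier trial in which "the mean (Standard deviation) values were 89.42 (7.16) and 71.7 (16.18) %, respectively", and derives an effect size of 1.416. With 5% alpha and 80% power it concludes that "the minimum estimated sample size was 9 subjects per group". The next sentence makes the allowance for loss: "Sample size was increased to 11 subjects per group to compensate for a dropout rate of 20% after 6 months".

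The study design text gives n=11 for each of the control and investigational groups. The treatment groups text agrees: "The sample will be divided into two groups according to laser application, 11 patients each group". So 11 is the number allocated, not the number expected to finish. The plan does not give the inflation formula, the sidedness of the test, or the name of the test.

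**The concern.** A reader will take the dropout sentence to mean that if a fifth of patients are lost, the required 9 per group will still be there. An allowance of that kind is normally obtained by dividing the required number by the proportion retained and rounding up. That route gives 12, not 11. If the sentence is wrong, the trial would reach its own planned dropout rate with slightly less than its own planned power, and the plan would be claiming a margin that it does not have. What is at stake is the accuracy of one statement, not the validity of the comparison.

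**Working it through.** **Inputs, all from the sample size section:** means 89.42 and 71.7; SDs 7.16 and 16.18; alpha 0.05; power 80%; minimum 9 per group; dropout 20%; 11 per group enrolled. **Assumed:** a two-sided, equal-variance two-sample t-test, with power from the noncentral t distribution.

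**1. Reproduce the plan's effect size.** Pooled SD = √[(7.16² + 16.18²)/2] = 12.51. Then d = (89.42 − 71.7)/12.51 = 17.72/12.51 = 1.416, as stated.

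**2. Reproduce the plan's minimum.** With n per group, df = 2n − 2 and noncentrality = d√(n/2):

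| n per group | Two-sided power |
|---|---|
| 8 | 75.0% |
| 8.8 (notional) | 79.5% |
| 9 | 80.5% |
| 11 | 88.4% |

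The smallest whole number reaching 80% is 9, matching the plan. A one-sided test would need only 7 (80.2%), so the stated 9 fits a two-sided test.

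**3. Check the dropout step.**
- Expected to remain from 11: 11 × 0.80 = 8.8, which is 0.2 of a patient below 9.
- Number needed to leave 9: 9/0.80 = 11.25, rounded up to 12. Twelve would leave 12 × 0.80 = 9.6.
- Largest loss per group that leaves 9: 11 − 9 = 2, and 2/11 = 18.2%. A third loss (3/11 = 27.3%) leaves 8.
- Multiplying instead of dividing gives 9 × 1.20 = 10.8, rounded up to 11. Rounding 11.25 down also gives 11. Either could be the source; the plan does not say, and neither leaves 9 after 20% loss.

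**4. Size of the shortfall.** On expected completers, 80.5% − 79.5% = 1.0 point. As a second basis, let each patient drop out independently (an assumption) and average power over the resulting group sizes. Starting from 11 per group, this gives 79.6% at 18.2% dropout and 78.5% at 20%, a difference of 1.1 points. On the same basis at 20% dropout, 12 per group gives 82.3%. The two bases agree that the gap between the rate that 11 covers and the stated rate is worth about 1 point.

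**The case against.** The strongest reply is that patients come whole. Twenty per cent of 11 is 2.2, and the nearest whole number, 2, leaves exactly 9. Over the trial, 20% of 22 is 4.4; the nearest, 4, leaves 18. No group of 11 can lose exactly 20%, and the 79.5% belongs to a group size that cannot occur. This is fair as a comment on scale: the point turns on a quarter of a patient per group. It does not rescue the sentence, because 2 of 11 is 18.2% and the plan says 20%.

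A second reply is that 80% power does not strictly require 9 in each group: 10 in one and 8 in the other also gives 80.0%. That is correct, so the limit of 2 losses per group applies to the stated minimum count, not to every split that holds 80% power. The room is slight, since 9 and 8 gives 77.8%.

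A third reply is that, with the test unnamed, tenths of a point are false precision. This also stands in part. With the two stated SDs at 9 per group, simulated power is about 80.4% for the pooled t-test and 77.9% for the Welch test, so the choice of test moves power by more than the dropout step does. That is a reason to name the test beside any power figure. It does not alter 11 × 0.80 = 8.8.

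**Conclusion.** The concern holds, as a minor matter of accuracy. The plan's effect size and minimum of 9 reproduce, but the statement that 11 per group compensates for 20% dropout does not follow from them, and nothing elsewhere in the document repairs it. The head-count shortfall needs no assumption about the test. The cost of about 1 point of power rests on a two-sided equal-variance t-test and on the cited trial's effect size. A change this small gives no reason to alter the design, the allocation or the number enrolled.

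**What to change.** Keep 11 per group and replace the dropout sentence with one on a single, stated basis, for example: *11 per group allows for up to 2 losses per group (18%) while keeping the minimum of 9 (80.5% power); at 20% dropout the expected 8.8 completers per group give about 79.5% power, assuming a two-sided equal-variance t-test.* If the planned analysis is a different test, the power figures should be recalculated for it.

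The same edit can tidy a clerical label: "β level of 0.8 (Power = 80"%) should give β as 0.2, since 80% power means β = 1 − 0.80. This has no bearing on the result.

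The cost is wording only, and one figure becomes slightly less favourable. The alternative, 12 per group, would make the existing claim true (9.6 expected completers, 83.3% power) at the price of 2 more patients, which a shortfall of this size does not warrant.
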